4. CLINICAL INVESTIGATION DESIGN

This clinical investigation is a multicentric prospective observational open-label, non-interventional clinical investigation evaluation, during the conventional clinical practice, the performance and safety of the daily instillation of Hyalistil Bio PF device in the treatment of patients affected by eye *discomfort* in particular in case of ocular dryness.

The clinical evaluation period was run approximately for 4 months from first patient first visit (FPFV) March 14th, 2023, to last patient last visit (LPLV) August 3rd, 2023. All patients were followed from enrolment until study end date, which was occur when, in compliance with the normal clinical practice, the last patient was undergo the Study Termination Visit (35± 4 days from the first instillation of study product).

4.1. Study visits and procedures

In this observational clinical investigation, each enrolled patient will be evaluated during 3 scheduled visits. A written informed consent will be obtained before any study assessment or procedure. The first patient first visit (FPFV) is defined as the 1st visit to the clinical site by the 1st screened patient. The “Last Patient Last Visit” (LPLV) is defined as the last visit to the clinical site by the last patient (i.e., the last visit foreseen by the study clinical investigation plan), independently of whether the patient completed or withdrew from the study.

Visit 1 (screening-enrolment)

The following procedures were performed:

- Explanation to the patient of study aims, procedures and possible risks of the observational study;
- Informed consent signature;
- Allocation screening number;
- Demographic data collection;
- In case of female patients (collection of information on pregnancy or breastfeeding self-reported by the patient);
- Medical and surgical history/current medical conditions;
- Prior/concomitant ocular and systemic medications;
- Ocular examination of both eyes:
 - o External Ocular Examination;
 - o BCVA test through the ETDRS at 4 m distance;
 - o Symptom Assessment in Dry Eye by SANDE questionnaire;

- Evaluation of Intraocular pressure (IOP);
- Tear film break-up time with fluorescein (TFBUT)[◊];
- Ocular surface staining (NEI score) with fluorescein;
- DEQS questionnaire administration:
 - Patient eligibility: inclusion/exclusion criteria evaluation;
 - Assignment of the study and allocation patient clinical investigational number;
 - Generation of unique subject identifiers code[□];
 - Medical device dispensation;
 - Beginning of the treatment*.

The Investigator will be dispensed to the patients 5 boxes of medical device each containing 30 single-dose containers of medical device for the following 35 ± 4 days. After completing the baseline evaluation, patients will start the study treatment as instructed through self-instillation of medical device under investigation at home*.

Patients were return to the clinical site on day 14 ± 2 from the first instillation of medical device under investigation (Visit 2).

Visit 2 (on the 14th day from the first instillation of medical device under investigation (MD)) (window ± 2 days)***

The following procedures will be performed:

- Assessment of treatment compliance;
- Current medical conditions;
- Concomitant medications;
- Evaluation of any reported adverse events/incidents**;
- Ocular examination of both eyes:
 - External Ocular Examination;
 - BCVA test through the ETDRS at 4 m distance;
 - Symptom Assessment in Dry Eye by SANDE questionnaire;
 - Evaluation of Intraocular pressure (IOP);
 - Tear film break-up time with fluorescein (TFBUT)[◊];
 - Ocular surface staining (NEI score) with fluorescein;

Patients were return to the clinical site on day 35 ± 4 days from the first instillation of medical device under investigation (Study Termination Visit).

Study Termination Visit (on the 35th day from the first instillation of medical device under investigation) (window ± 4 days)

The final visit is defined as the visit performed on 35 ± 4 days after the first instillation of medical device under investigation[○].

In case of premature study discontinuation, patients will undergo an Early Termination Visit (ETV):

The following procedures will be performed:

- Assessment of treatment compliance (reconciliation of the amount of used single dose containers and empty/unused medical device boxes returned by patients to the centre)[§];
- Current medical conditions;

- Concomitant medications;
- Evaluation of any reported adverse events/incidents**;
- Ocular examination of both eyes:
 - o External Ocular Examination;
 - o BCVA test through the ETDRS at 4 m distance;
 - o Symptom Assessment in Dry Eye by SANDE questionnaire;
 - o Evaluation of Intraocular pressure (IOP);
 - o Tear film break-up time with fluorescein (TFBUT)[◊];
 - o Ocular surface staining (NEI score) with fluorescein;
- Administration of the VAS scale on the degree of satisfaction to the treatment;
- DEQS questionnaire administration;
- Evaluation of the safety of the experimental product through the compilation of the IGAS scale;
- Restitution of remaining medical devices [§].

* Start of the treatment (window + 1 day).

** In case of adverse events/incidents all assessments considered necessary by the Investigator was performed, including the possible suspension of treatment.

*** Variable because it is based on the planned visit schedule according to clinical practice for the individual patient Visit 2 (windows of \pm 2 days).

° All patients enrolled were treated for 35 days. The Study Termination Visit is variable because it is based on the planned visit schedule according to clinical practice for the individual patient (window \pm 4 days).

§ Restitution of the amount of used single dose containers and empty/unused medical device boxes returned by patients to the centre.

In case of premature study discontinuation, patients were undergoing an Early Termination Visit (ETV). During the ETV the patients will return the amount of used single dose containers and empty/unused medical device boxes returned by patients to the centre:

The “unique subject identifiers code” consists of the 5-digit screening number (e.g. S1001, S1002,...S1028 etc.), and, if applicable, the 4-digit subject clinical investigational number (e.g. 1001, 1002,...1028 etc.). Specifically, the first subject clinical investigational number was referred to the study site.

Allocation screening number and subject clinical investigational number are separated by slashes (e.g. “S1001/1001”). (e.g. “S1001/1001” for site number 1, “S2001/2001” for site number 2).

◊ The TFBUT value will be recorded as the average of 3 measurements.

4.2. Treatment Administration

All patients meeting the inclusion and exclusion criteria

4.3. Randomization and Blinding

Not applicable: open-label clinical investigation

4.4. Clinical Investigation Scheme

Study Procedure	Visit 1 (screening- enrolment- start of treatment)*	Visit 2*** (on the 14 th day from the first instillation of medical device) (window ± 2 days)	Study termination Visit ^o (on the 35 th day from the first instillation of medical device) (window ± 4 days)
Informed Consent	√		
Allocation screening number	√		
Demographic data collection	√		
Medical and surgical history	√		
Current medical conditions	√	√	√
Prior ocular local and systemic medication	√		
Concomitant ocular local and systemic medication		√	√
External Ocular Examination	√	√	√
BCVA evaluation through ETDRS grade	√	√	√
SANDE questionnaire	√	√	√
Evaluation of Intraocular pressure (IOP)	√	√	√
Ocular surface staining (Fluorescein- NEI score)	√	√	√
Tear Film Break-up Time^φ (TFBUT- Fluorescein)	√	√	√
Administration of DEQS^{###} questionnaire	√		√
Inclusion/Exclusion Criteria	√		

Hyalistil Bio PF Mono*Medical device***Study code: 052/SI Hyalistil Bio PF Mono**

Enrolment and allocation subject clinical investigational number	√		
Generation of unique subject identifiers code[□]	√		
Medical device dispensing*	√		
Check Compliance (check proper treatment with medical device, use of other medication and medical devices)		√	√
Medical device restitution[§]'			√
Evaluation of satisfaction to the treatment by VAS scale			√
Evaluation of IGAS			√
Adverse events /Incidents**		√	√

* Start of the treatment (window + 1 day).

** In case of adverse events/incidents all assessments considered necessary by the Investigator will be performed, including the possible suspension of treatment.

*** Variable because it is based on the planned visit schedule according to clinical practice for the individual patient Visit 2 (windows of \pm 2 days).

° All patients enrolled will be treated for 35 ± 4 days. The Study Termination Visit is variable because it is based on the planned visit schedule according to clinical practice for the individual patient (window \pm 4 days).

§ Restitution of the amount of used single dose containers and empty/unused medical device boxes returned by patients to the centre.

'In case of premature study discontinuation, patients will undergo an Early Termination Visit (ETV). During the ETV the patients will return the amount of used single dose containers and empty/unused medical device boxes returned by patients to the centre

□ The “unique subject identifiers code” consists of the 5-digit screening number (e.g. S1001, S1002,...S1028 etc.), and, if applicable, the 4-digit subject clinical investigational number (e.g. 1001, 1002,...1028 etc.). Specifically, the first subject clinical investigational number was referred to the study site.

Allocation screening number and subject clinical investigational number are separated by slashes (e.g. “S1001/1001”). (e.g. “S1001/1001” for site number 1, “S2001/2001” for site number 2).

◊ The TFBUT value will be recorded as the average of 3 measurements.

###In the event that, for both trial centers, the DEQS questionnaire is not available, the assessment of the quality of the life will be performed by the DEQ-5 questionnaire.

5. PRIMARY AND SECONDARY OUTCOMES[^]

5.1. Primary Endpoints[#]

- *Clinical performance:*

-25 % increase from Visit 1 (*Day 0 of treatment - baseline*) to Study Termination Visit (*Day 35 ± 4 of treatment*) of tear film break-up time with fluorescein (TFBUT)[◊] [Time frame: Visit 1 and Study Termination Visit].

For more details see paragraph 13 and the list and samples of tables, figures and graphs, reported in paragraph 15.

5.2. Secondary Endpoints

- Reduction from baseline (*Visit 1- Day 0 of treatment*) in the corneal and conjunctival fluorescein staining score using the NEI scale.

Fluorescein staining of the ocular surface is assessed as the total sum of the corneal and conjunctival subregions.

- Corneal Fluorescein Staining (NEI score, sum of 5 subregions, maximum score 15. Each subregion will have a maximum score of 3.

(0=no staining, 3 = maximum staining).

- Conjunctival Fluorescein Staining (NEI score, sum of 6 subregions, maximum score 18. Each subregion will have a maximum score of 3.

(0=no staining, 3 = maximum staining).

[Time frame: Visit 1, Visit 2 and Study Termination Visit].

- Tear film break-up time with fluorescein (TFBUT)[◊]. [Time frame: Visit 2 and Study Termination Visit].

- BCVA is measured using the standard Early Treatment Diabetic Retinopathy Study (ETDRS) acuity chart and reported in ETDRS letters. [Time frame: Visit 1, Visit 2 and Study Termination Visit];

- *Patient reported outcomes:*

Change in intensity^{##} and frequency of dry eye symptoms assessed by completing the questionnaire SANDE. [Time frame: Visit 1, Visit 2 and Study Termination Visit].

^{##}In the questionnaire SANDE, the term "intensity" has the same meaning than "severity".

- ^{###}Evaluation of the degree of satisfaction to the treatment reported by patients through the use of the visual analogue scale (VAS) ^{###}, ranging from 0 to 100 mm, at Study Termination Visit (*Day 35 ± 4 of treatment*). [Time frame: Study Termination Visit].

Patients will be asked to rate their degree of satisfaction to the treatment and answer the following questions:

- “I feel satisfied using this treatment? ”,
- “With this treatment, I have a feeling of freshness?”,
- “With this treatment, I have a feeling of relief?”,

Study code: 052/SI Hyalistil Bio PF Mono

- “This treatment contributed to reduce my pain due to eye dryness?”,
- “This treatment is comfortable? ”,

Patients will be asked to place a vertical mark on a horizontal line, from 0 to 100 mm, to indicate the degree of satisfaction to the treatment, where:

- ✓ 0-10 mm=none
- ✓ 11-30 mm=very mild
- ✓ 31-50 mm=mild
- ✓ 51-70 mm=moderate
- ✓ 71-90 mm=strong
- ✓ 91-100 mm=very strong.

- Assessment of the quality of life (QOL) by “Questionnaire about Eye Symptoms and Daily Life” (DEQS) at Study Termination Visit (Day 35 ± 4 of treatment) compared to Visit 1 (Day 0 of treatment - baseline). [Time frame: Visit 1 and Study Termination Visit].

For more details see paragraph 13 and the list and samples of tables, figures and graphs, reported in paragraph 15.

~~###In the event that, for both trial centers, the DEQS questionnaire is not available, the assessment of the quality of the life will be performed by the DEQ 5 questionnaire.~~

According to clinical practice, the Investigator will perform all clinical evaluations on both eyes of the individual patient.

In the case that both eyes are affected by ocular dry eye, the statistical analysis will be performed considering the eye with the lowest level of TFBUT score “worse eye”. If the level of TFBUT score at baseline is the same in both eyes, then the eye with the highest level of NEI score will be designated as the “worse eye”. If the level of NEI score at baseline is the same in both eyes, then the right eye will be designated as the “worse eye.”

5.3. Safety Endpoints

Evaluation of safety parameters

Evaluation of safety of daily instillation of ophthalmic solution during all the study period through:

- Evaluation of safety of daily instillation of ophthalmic solution during all the study period through:
 - Investigator Global Assessment of Safety (IGAS): using the 4-point scale: 1= very good safety, 2 =good safety, 3 = moderate safety and 4 = poor safety. IGAS will be evaluated at the Study Termination Visit. [Time Frame: Study Termination Visit];
 - Evaluation of reported adverse events/incidents. [Time Frame: During the treatment period].
- Evaluation of intraocular pressure (IOP) [Time frame: Visit 1, Visit 2 and Study Termination Visit];
- Evaluation of *compliance* through verification of correct instillation of the medical device,

Study code: 052/SI Hyalistil Bio PF Mono

counting of single dose containers and boxes. [Time Frame: Visit 2 and Study Termination Visit].

[^]According to clinical practice, the Investigator will perform all clinical evaluations on both eyes of the individual patient.

The statistical analysis will be performed considering right eye as the “study eye.”

#The primary end point will be evaluated on the ITT population and in PP population.

†The TFBUT value will be recorded as the average of 3 measurements.

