§ Restitution of the amount of used single dose containers and empty/unused medical device boxes returned by patients to the centre.

'In case of premature study discontinuation, patients will undergo an Early Termination Visit (ETV). During the ETV the patients will return the amount of used single dose containers and empty/unused medical device boxes returned by patients to the centre'

* The "unique subject identifiers code" consists of the 5-digit screening number (e.g. S1001, S1002,...S1028 etc.), and, if applicable, the 4-digit subject clinical investigational number (e.g. 1001, 1002,...1028 etc.). Specifically, the first subject clinical investigational number was referred to the study site.

Allocation screening number and subject clinical investigational number are separated by slashes (e.g. "S1001/1001"). (e.g. "S1001/1001" for site number 1, "S2001/2001" for site number 2).

† The TFBUT value will be recorded as the average of 3 measurements.

19. Primary and secondary outcomes[^]

Primary Endpoints[#]

- *Clinical performance:*

-25 % increase from Visit 1 (*Day 0 of treatment - baseline*) to Study Termination Visit (*Day 35 ± 4 of treatment*) of tear film break-up time with fluorescein (TFBUT)f. [Time frame: Visit 1 and Study Termination Visit].

Secondary Endpoints

- Reduction from baseline (*Visit 1- Day 0 of treatment*) in the corneal and conjunctival fluorescein staining score using the NEI scale.

Fluorescein staining of the ocular surface is assessed as the total sum of the corneal and conjunctival subregions.

- Corneal Fluorescein Staining (NEI score, sum of 5 subregions, maximum score 15. Each subregion will have a maximum score of 3.

(0=no staining, 3 = maximum staining).

- Conjunctival Fluorescein Staining (NEI score, sum of 6 subregions, maximum score 18. Each subregion will have a maximum score of 3.

(0=no staining, 3 = maximum staining).

[Time frame: Visit 1, Visit 2 and Study Termination Visit].

- Tear film break-up time with fluorescein (TFBUT)[◊]. [Time frame: Visit 2 and Study Termination Visit].

- BCVA is measured using the standard Early Treatment Diabetic Retinopathy Study (ETDRS) acuity chart and reported in ETDRS letters. [Time frame: Visit 1, Visit 2 and Study Termination Visit];

- *Patient reported outcomes:*

- Change in intensity and frequency of dry eye symptoms assessed by completing the questionnaire SANDE. [Time frame: Visit 1, Visit 2 and Study Termination Visit].

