3.3. Safety Evaluations

- Evaluation of safety of daily instillation of ophthalmic solution during all the study period through:
 - ✓ Investigator Global Assessment of Safety (IGAS): using the 4-point scale: 1 = very good safety, 2 = good safety, 3 = moderate safety and 4 = poor safety. IGAS was evaluated at the Study Termination Visit. [Time Frame: Study Termination Visit];
 - ✓ Evaluation of reported adverse events/incidents. [Time Frame: During the treatment period];
 - ✓ Evaluation of intraocular pressure (IOP) [Time frame: Visit 1, Visit 2 and Study

Termination Visit];

According to clinical practice, the Investigator will perform all clinical evaluations on both eyes of the individual patient.

In the case that both eyes are affected by ocular dry eye, the statistical analysis will be performed considering the eye with the lowest level of TFBUT score “worse eye”. If the level of TFBUT score at baseline is the same in both eyes, then the eye with the highest level of NEI score will be designated as the “worse eye”. If the level of NEI score at baseline is the same in both eyes, then the right eye will be designated as the “worse eye.”

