13 ANALYSIS OF PERFORMANCE

13.1 Primary performance endpoint

The primary endpoint consists in the assessment of 25 % increase from Visit 1 (*Day 0 of treatment - baseline*) to Study Termination Visit (*Day 35 ± 4 of treatment*) of tear film break-up time with fluorescein (TFBUT)^ø. The data will be reported (change vs baseline) as minimum, maximum, mean, standard deviation or median and IQR. According to the data distribution, paired t-test or Wilcoxon signed-rank test will be used to test the statistical significance of the change from baseline to each time points. [Time frame: Visit 1, and Study Termination Visit].

Patients with a Tear Film Break-up Time TFBUT test ≤ 10 in the study eye (study eye) at the screening visits are eligible for enrollment.

TFBUT will be measured by determining the time to tear break-up. The TFBUT will be performed after instillation of 5 μl of 2% preservative-free sodium fluorescein solution into the inferior conjunctival cul-de-sac of each eye. The patient will be instructed to blink several times to thoroughly mix the fluorescein with the tear film. To achieve maximum fluorescence, the examiner should wait approximately 30 seconds after instillation before evaluating TFBUT.

With the aid of a slit lamp at 10X magnification using cobalt blue illumination, the examiner will monitor the integrity of the tear film, noting the time it takes to form lacunae (clear spaces in the tear film) from the time that the eye is opened after the last blink. This measurement will be performed within 10 seconds maximum. The TFBUT will be measured twice during the first minute after the instillation of the fluorescein. The TFBUT value will be the average of 3 measurements.

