4 PERFORMANCE DATA (PRIMARY ENDPOINTS)

Table 4.1.1 TFBUT ITT population (v1) vs (v3)

Table 4.1.2 Delta % TFBUT ITT population (v1) vs (v3)

Table 4.2.1 TFBUT PP population (v1) vs (v3)

Table 4.2.2 Delta % TFBUT PP population (v1) vs (v3)

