5 PERFORMANCE DATA (SECONDARY ENDPOINTS)

-NEI Scale ITT population

Table 5.1.1 TOTAL SCORE NEI ITT population (v1) vs (v3)

Table 5.2.1 TOTAL SCORE NEI ITT population (v1) vs (v2)

Table 5.3.1 TOTAL SCORE CORNEA ITT population (v1) vs (v3)

Table 5.3.2 TOTAL SCORE CORNEA ITT population (v1) vs (v2)

Table 5.4.1 TOTAL SCORE CONJUNCTIVA ITT population (v1) vs (v3)

Table 5.4.2 TOTAL SCORE CONJUNCTIVA ITT population (v1) vs (v2)

-TFBUT ITT POPULATION

Table 5.5.1 TFBUT ITT population (v1) vs (v2)

-Questionnaire SANDE ITT population

Table 5.6.1 TOTAL SCORE SANDE ITT population (v1) vs (v3)

Table 5.7.1 TOTAL SCORE SANDE ITT population (v1) vs (v2)

Study code: 052/SI Hyalistil Bio PF Mono

Table 5.8.1 SEVERITY DRYNESS/IRRITATION ITT population (v1) vs (v3)

Table 5.8.2 SEVERITY DRYNESS/IRRITATION ITT population (v1) vs (v2)

Table 5.9.1 FREQUENCY DRYNESS/IRRITATION ITT population (v1) vs (v3)

Table 5.9.2 FREQUENCY DRYNESS/IRRITATION ITT population (v1) vs (v2)

-Questionnaire VAS ITT population

Table 5.10.1 Question "I feel satisfied using this treatment? ", ITT population

Table 5.10.2 Question "With this treatment, I have a feeling of freshness?", ITT population.

Table 5.10.3 Question "With this treatment, I have a feeling of relief?", ITT

Table 5.10.4 Question "This treatment contributed to reduce my pain due to eye dryness?", ITT population

Table 5.10.5 Question "This treatment is comfortable? ", ITT population

Table 5.10.6 Total score VAS, ITT population

-DEQS ITT POPULATION

Table 5.11.1.1 DEQS Summary score ITT population (v1) vs (v3)

Table 5.11.2.1 DEQS Bothersome Ocular Symptoms subscale ITT population (v1) vs (v3)

Table 5.11.3.1 DEQS Impact on Daily Life subscale ITT population (v1) vs (v3)

Table 5.11.4.1 DEQS-GES ITT population (v1) vs (v3)

-IGAS

Table 5.12.1 IGAS ITT populations

-IOP ITT POPULATION

Table 5.13.1 IOP ITT population (v1) vs (v3)

Table 5.14.1 IOP ITT population (v1) vs (v2)

Study code: 052/SI Hyalistil Bio PF Mono

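### The protocol and the SAP each give two conflicting study-eye rules, so the primary TFBUT analysis (and the NEI and IOP analyses) is not uniquely defined

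*SAP*

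**What the plan says.** **Worse-eye rule.** SAP 3.3 reads "In the case that both eyes are affected by ocular dry eye, the statistical analysis will be performed considering the eye with the lowest" TFBUT. Equal TFBUT is broken by the higher NEI score, and equal NEI by taking the right eye. SAP 5.2 repeats it: "the statistical analysis will be performed considering the eye with the lowest level of TFBUT score". The protocol synopsis gives the same rule in the ^ note to its endpoints.

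**Right-eye rule.** The ^ note closing SAP section 5 says "The statistical analysis will be performed considering right eye as the" study eye. Protocol section 19 ends with the same sentence. Neither attaches a condition.

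**Reach.** In the SAP the sentence is printed under 5.3 (safety), but the ^ mark sits on the section 5 heading, "PRIMARY AND SECONDARY OUTCOMES". The heading of protocol section 19 carries the same mark.

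**Where the rule would be applied.** SAP 13.1 says only that patients with TFBUT of 10 or less "in the study eye (study eye) at the screening visits are eligible for enrollment". The table list in SAP 15.2 gives one comparison per endpoint and visit pair, for example "Table 4.1.1 TFBUT ITT population (v1) vs (v3") and "Table 5.13.1 IOP ITT population (v1) vs (v3"), and names no eye. SAP 6.2 says the final analysis follows both the SAP and protocol version 2.

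**The concern.** The primary result is a before-after change in one eye per patient, with no control arm, so the choice of eye is the choice of data. Two analysts who each follow the plan could report different TFBUT, NEI and IOP results, and neither would have departed from it. Both eyes are measured at every visit and the study is open-label, so an open rule leaves a choice between two sets of results.

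The same ambiguity enters eligibility. Protocol section 6 admits disease in one or both eyes, while protocol section 20 and SAP 13.1 tie the TFBUT limit to the study eye. SAP 11.2 makes failure of an inclusion criterion a ground for leaving the per-protocol set, and protocol section 23 runs the primary analysis on that set before repeating it in the ITT population.

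**Working it through.** **1. Can the passages be read together?**

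| Reading | Why it fails |
|---|---|
| The right eye is only the last tie-break | True in the synopsis, SAP 3.3 and SAP 5.2. In protocol 19 and the SAP section 5 footnote it is unconditional. |
| The right-eye sentence is for safety only | The ^ mark is on the outcome headings. The same SAP footnote block also holds the note on populations for the primary endpoint and the note on averaging TFBUT. |
| The right eye is the default for unilateral disease | Nothing says so, and with left-only disease it would select the unaffected eye. |
| Another section decides | SAP 13.1 does not define the study eye, SAP 9.1 lists right- and left-eye TFBUT fields without a selection rule, and SAP 6.2 points to a protocol with the same conflict. |

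There is also a gap in the worse-eye rule: it is written only for patients with both eyes affected. For one affected eye, that eye is implied but not stated.

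**2. Sample size.** Inputs from protocol 23 and SAP 7: mean change 1.56 s, SD 1.91 s, two-sided alpha 0.01, power 0.80. The standardised effect is 1.56/1.91 = 0.817. A paired t calculation gives n = 21; dividing by the Wilcoxon efficiency 0.955 gives 22. Simulating the exact signed-rank test with normal changes gives power 0.829 at n = 23. The stated 23 is reproduced to within two patients, and 23 × 1.2 = 27.6 rounds up to the stated 28. No eye-selection input enters, so these figures are the same under either rule.

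**3. How often the rules disagree.** Assume that in a bilateral patient either eye is equally likely to be the worse one.
- All 28 bilateral, no ties: 28 × 0.5 = 14; central 95% range of Binomial(28, 0.5) = 9 to 19.
- 10% tied on both TFBUT and NEI (assumed): 28 × 0.9 / 2 = 12.6.
- 23 evaluable patients: 23 × 0.5 = 11.5.

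**4. Can picking the worse eye move the estimate by itself?** Let S be the baseline SD, ρ the inter-eye correlation and R the within-eye test-retest reliability. With normal data, independent errors and no true effect, the expected change in the eye with the lower baseline is S(1 − R)/√(π(1 − ρ)). S = 1.75 s comes from the plan; ρ and R are assumptions.
- ρ = 0.5, R = 0.9: 1.75 × 0.1/√(π × 0.5) = 0.14 s.
- ρ = 0.7, R = 0.7: 1.75 × 0.3/√(π × 0.3) = 0.54 s.

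For a fixed right eye the expected change is 0. This shows only that the two rules need not agree; it is not an estimate for this study.

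**The case against.** The best reply is that the harm is unmeasured. If both eyes are treated and exchangeable, the rules differ in expectation only through regression to the mean, and its size needs correlations that the documents do not give. Either rule could be made coherent, and the worse-eye rule favours an apparent improvement in an uncontrolled study. All of this stands. It limits what can be claimed about size, and it is why a sensitivity analysis belongs in the fix, but it does not reconcile the two sentences.

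Several stronger readings are tempting and should not be drawn:
- *The right-eye rule would dilute the effect by analysing untreated eyes in left-only patients.* The share of such patients is not given. If the right eye is the study eye, a left-only patient whose right eye exceeds 10 s does not meet the eligibility sentence in protocol 20 and SAP 13.1. Protocol 14.1 directs the drops to the affected eye, but the synopsis dosage has no such limit and protocol 15 says one container serves both eyes. The documents therefore do not show that unaffected eyes went untreated, and no diluted figure can be supported.
- *The eye was chosen after seeing results.* SAP version 1 is dated October 10th, 2023, 68 days after the last visit on August 3rd (28 + 30 + 10). Nothing shows that results had been examined, and SAP 6.2 describes database lock as still to come.
- *Every endpoint is affected.* BCVA has one field with no eye label in SAP 9.1 and no table in SAP 15.2. SANDE is scored once for both eyes together (SAP 13.2).
- *One rule is a leftover from an amendment.* The available text cannot show this. Both rules stand in current text.

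**Conclusion.** The contradiction is certain: it can be read directly in both documents, it reaches the primary endpoint, and no passage gives precedence. The primary TFBUT analysis and the NEI and IOP analyses therefore depend on an unstated choice of eye, and for some patients eligibility and per-protocol status may too.

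The only size that can reasonably be attached is the rate of disagreement, about half of bilateral patients. It rests on exchangeable eyes with few ties, and the count of about 14 of 28 also assumes that all patients are bilateral. How far the estimated change would move cannot be derived from the documents. The point merits correction because it concerns the primary endpoint and is cheap to settle.

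**What to change.** State one study-eye rule in the SAP and refer to it in 13.1: the qualifying eye if only one eye qualifies; if both do, the worse eye with the existing tie-breaks. This rule is the more detailed of the two, is stated more often, and does not select an unaffected eye. Use the same definition wherever eligibility or per-protocol membership refers to the study eye.

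Delete the unconditional right-eye sentence from the SAP section 5 footnote. For protocol section 19, either amend it under protocol 22.4 or record the difference in both the SAP and the study report. SAP 14 alone does not cover this, because it concerns departures from the SAP.

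Add a planned sensitivity analysis of the primary endpoint on the right eye or on the mean of both qualifying eyes, because choosing the lower baseline can add regression to the mean when there is no control.

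Do this before database lock. If lock has already occurred, record it as a documented change and show the results under both rules.

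Cost: a few lines in the SAP and one extra table. If the protocol is aligned, add a written, reasoned and signed amendment sent to the ethics committees. No new measurements are needed for TFBUT, NEI or IOP, since SAP 9.1 already lists fields for both eyes.
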